14.0 Potential Benefits to Participants

- 14.1 **Potential Benefits:** There may be a short-term benefit in movement function from a single-session of tDCS, as described in other studies.^{17, 18} However, this benefit is not expected in our participants with UCP, nor is the objective of the study to improve movement function or control.

There is no direct benefit to CTD from participation in this study. We do not expect a single-session of tDCS to significantly alter movement function in these children, however improvements in motor learning have been demonstrated in CTD following tDCS.¹⁴ The safety of tDCS has been clearly demonstrated in children ages 7-21 in our previous work¹⁹ (and [name] et al. In Review) and other systematic reviews.^{16, 20, 21} Therefore, we justify using CTD in our study as a scientifically-sound comparison group.

15.0 Data Management

- 15.1 **Data Analysis Plan:** Baseline and demographic information will be summarized by descriptive statistics for continuous variables, and the number and percentage of participants in each category for categorical variables. The primary analysis will compare changes in behavioral and neurophysiologic measures between the two intervention groups (real and sham tDCS). When possible, we will use repeated measures ANOVA to account for differences between groups. If measures are non-normally distributed, we will use Wilcoxon signed-ranks tests. We will use correlation analysis to compare modeled peak electric field strength with changes in behavioral and neurophysiologic outcomes.

Summary of power analysis with alpha of 0.0125 and N per group of 8			
Correlation	MEP		
	Δ	SD	Power
0.3	0.75	0.5	0.71
0.4	0.75	0.5	0.75
0.5	0.75	0.5	0.81
0.6	0.75	0.5	0.87
0.7	0.75	0.5	0.94

- 15.2 **Power Analysis:** With the data and literature available, we completed power calculations for the primary neurophysiological outcome, MEP, and the behavioral clinical outcome, the Assisting Hand Assessment (AHA) scaled score (Table 2). These were based on the difference between the pre- and post-test measurements

adjusting for baseline values, similar to ANCOVA analyses, for added precision. These calculations used the sample size formula for normally distributed statistics with a Bonferroni corrected type I error level of 0.0125 for the four potential primary comparisons between the: 1) Anodal Ipsilesional tDCS group versus Sham_c tDCS, 2) Cathodal Contralesional tDCS versus Sham_c tDCS, 3) Anodal Ipsilesional tDCS group versus Cathodal Contralesional tDCS, and 4) Anodal Contralesional tDCS versus Sham_i tDCS to maintain an overall type I error level of 0.05. Power was computed for 8 participants per treatment group across a range of possible values for the correlation between pre- and post-treatment measurements. These were computed for a change in the MEP of 0.75 mV. The mean change and standard deviation of the MEP in the study population was based on the tDCS/CIMT study. The correlation between pre- and post-treatment MEP in the tDCS/CIMT study was approximately 0.5. Based on these estimates, we will have 81% power to detect a change in the MEP of 0.75 mV, which translates into a large effect size (Cohen's $d = 1.5$).

15.3 Statistical Analysis: Descriptive analyses of baseline characteristics and outcomes will include means and standard deviations for continuous variables and frequencies for categorical variables. Compliance and tolerance of the intervention will also be evaluated. Safety analyses will be primarily descriptive reporting the number and percentage of any adverse events and will be evaluated and monitored throughout the trial.

This analysis will be conducted based on the intent-to-treat principle to compare the mean neurophysiologic change measured using the MEP from pre- to post- intervention between each tDCS stimulation dose group and sham tDCS adjusted for baseline neurophysiologic measures. Confidence intervals and p-values will be based on robust variance estimation. Statistical significance will be considered as $p < 0.0125$. Supportive analyses may be conducted with consideration of adjustment for residual imbalances between treatment groups after randomization (e.g., gender). The primary analysis will evaluate the change between pre- and post- measurements. A secondary analysis will evaluate the change between pre- and 30 minutes post.

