3.0 Study Endpoints/Events/Outcomes

- 3.1 Primary Endpoint/Event/Outcome: The primary outcome is magnitude of brain excitability as measured by motor evoked potentials from TMS. The primary behavioral outcome is time to complete a novel movement task.
- 3.2 Secondary Endpoint(s)/Event(s)/Outcome(s): The secondary neurophysiological outcomes are interhemispheric inhibition as measured by ipsilateral silent period (iSP) and paired pulse (PP) TMS (see 5.2 Study Procedures). The secondary behavioral outcomes are the Box and Blocks Test and Grip Strength. Safety and tolerability of the study, as measured through our participant-report of symptoms questionnaires, are also secondary outcomes.

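### Baseline adjustment is written for MEP only; task time and the continuous secondary outcomes are left to a repeated measures ANOVA of changes without a baseline covariate, and MEP itself has two stated methods

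*Combined protocol and SAP*

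**What the plan says.** Section 3.1 names MEP magnitude as the primary outcome and adds a behavioral one: "The primary behavioral outcome is time to complete a novel movement task". Section 3.2 lists iSP, paired pulse, Box and Blocks and grip strength as secondary, together with safety and tolerability.

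Section 15.1 covers both domains: "The primary analysis will compare changes in behavioral and neurophysiologic measures between the two intervention groups (real and sham tDCS"). The method is "When possible, we will use repeated measures ANOVA to account for differences between groups", with the fallback "If measures are non-normally distributed, we will use Wilcoxon signed-ranks tests". Neither sentence names a baseline covariate, the ANOVA term to be tested, or the post time that counts.

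Section 15.3 is more specific but narrower. Its analysis will "compare the mean neurophysiologic change measured using the MEP from pre- to post- intervention", comparing each stimulation group with sham, "adjusted for baseline neurophysiologic measures", with robust variance estimation. The only other adjustment there is optional, supportive and aimed at residual imbalance.

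Section 15.2 says that its calculations, for MEP and for the AHA scaled score, rest on the pre-to-post difference, "adjusting for baseline values, similar to ANCOVA analyses, for added precision".

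Section 5.2 schedules TMS and behavioral assessments before the intervention and at 0, 15, 30 and 60 minutes after it.

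**The concern.** The plan recognizes that adjusting for baseline buys precision and uses it when computing power, but writes it into the analysis of one outcome only. Task time carries the motor-performance half of Aim 2, with about 8 children per group. Its pre-test value is collected anyway, and nothing in the analysis plan uses it as a covariate. The same holds for the continuous secondary outcomes.

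There is also an ambiguity over MEP. Section 15.1 applies to neurophysiologic measures, so MEP falls under the 15.1 ANOVA and also under the 15.3 adjusted comparison. The two can give different p-values from the same data, and the plan does not say which one decides.

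**Working it through.** **Inputs from section 15.2.** 8 per group; MEP difference 0.75 mV; SD 0.5; alpha 0.0125; pre-post correlation r of about 0.5, tabulated from 0.3 to 0.7. No difference, SD or correlation is given for task time.

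**Variances at one post time, in units of SD².**
- Change score: 2(1 − r). At r = 0.5 this is 1.00.
- Baseline as covariate: 1 − r². At r = 0.5 this is 0.75.
- Ratio: 2/(1 + r), which is 1.54 at r = 0.3, 1.33 at 0.5 and 1.18 at 0.7.

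With two time levels, the group-by-time term of a repeated measures ANOVA is the change-score test.

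**Step 1: which variance lies behind the plan's power table?** At r = 0.5 the adjusted SD is 0.5 × √0.75 = 0.433, the standard error is 0.433 × √(2/8) = 0.217, and 0.75/0.217 = 3.46. For the change score, the SD is 0.5 × √1.00 = 0.5, the standard error is 0.25, and 0.75/0.25 = 3.00.

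| r | Plan | Covariate, one-sided t (13 df) | Covariate, two-sided normal | Change score, two-sided normal |
|---|---|---|---|---|
| 0.3 | 0.71 | 0.724 | 0.741 | 0.515 |
| 0.4 | 0.75 | 0.761 | 0.781 | 0.595 |
| 0.5 | 0.81 | 0.811 | 0.833 | 0.692 |
| 0.6 | 0.87 | 0.872 | 0.895 | 0.804 |
| 0.7 | 0.94 | 0.938 | 0.956 | 0.915 |

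The table follows the covariate variance, not the change-score variance. The closest variant is a one-sided t test, although 15.2 describes a normal formula and states no sidedness; a two-sided t test would give 0.707 at r = 0.5. On the MEP inputs at r = 0.5, leaving out the covariate costs 0.833 − 0.692 = 14 points (two-sided normal), or 0.811 − 0.687 = 12 points (one-sided t). Equal precision without it would need 8 × 2/(1 + 0.5) = 10.7 per group.

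**Step 2: illustration for an outcome such as task time.** This borrows the MEP correlations and uses 8 v 8, two-sided 0.05 and one post time. For the change score the noncentrality is d/(√(2(1 − r)) × √(2/8)). At r = 0.5 and d = 1.0 it is 1.0/(1.0 × 0.5) = 2.0, which on 14 df gives 46%. For the covariate model it is 1.0/(0.866 × 0.5) = 2.31, which on 13 df gives 57% before allowing for chance baseline imbalance. Simulation, which includes that imbalance, gives 54%, and the simulated figure is used below.

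| r | Effect | Change score | Pre-test as covariate |
|---|---|---|---|
| 0.3 | 1.0 SD | 35% | 47% |
| 0.5 | 1.0 SD | 46% | 54% |
| 0.5 | 1.5 SD | 80% | 87% |
| 0.7 | 1.0 SD | 67% | 70% |
| 0.7 | 1.5 SD | 95% | 96% |

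Repeat simulations agree to about one point.

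**The case against.** The strongest reply is that nothing here is invalid. Section 15.1 compares changes, so the baseline difference is removed by subtraction, and in a randomized comparison that is unbiased. This stands: the point concerns precision and specification, not bias.

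A reader might infer more in four places.

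- **That the behavioral analysis contradicts its own power basis.** The behavioral calculation in 15.2 is for AHA, which section 3 lists as neither primary nor secondary. Task time has no power basis to contradict, and the 0.5 is an MEP correlation.
- **That every non-MEP outcome goes to the ANOVA.** Safety is descriptive, electric field strength is handled by correlation, and non-normal measures go to Wilcoxon tests.
- **That the loss is very large with four post times.** At r = 0.5 and a constant 1.0 SD effect, a group-by-time test over all five times has 46% power and a baseline-adjusted mean of the post values 83%. These are different contrasts. An unadjusted change score on the same post mean already reaches about 65%, and the adjusted 0-minute test only about 54%. At r = 0.7 the group-by-time test does as well as the adjusted 0-minute test: about 71% v 70% for a constant effect, and 97% v 96% for one fading from 1.5 SD to zero. Nor does 15.1 say that all five times enter one model.
- **That the test might be a group main effect averaging in the pre-test.** Section 15.1 commits to comparing changes, so this is not a fair reading.

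One could also argue that 15.3 is meant to reach iSP and paired pulse, since its covariate is worded for neurophysiologic measures generally. But it names MEP as the measure of change, and no reading extends it to behavior.

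**Conclusion.** The point holds as a modest, low-cost improvement together with one inconsistency to resolve. No baseline covariate is written for task time, Box and Blocks, grip strength, iSP or paired pulse, and MEP has two methods with no stated order.

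Like for like at one post time, the covariate is worth about 7 to 8 points of power at correlation 0.5, about 12 points at 0.3 (1.0 SD) and 1 to 3 points at 0.7. At the plan's alpha of 0.0125 with the MEP inputs, it is worth 12 to 14 points at 0.5. These figures assume 8 per group, equal SDs before and after, normal data and MEP correlations carried over to other outcomes. The actual gain for task time cannot be computed from the documents.

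**What to change.** - In 15.1, replace the repeated measures ANOVA for task time and the continuous secondary outcomes with the 15.3 model: post value on arm, with that outcome's own pre-test value as covariate. Put the pre-to-post contrast first, and name which of the four post times it uses.
- For the time course, use a mixed model on the post times with the pre-test as covariate. A child who misses one post assessment then stays in the analysis.
- State that MEP follows 15.3 only.
- In 15.2, state the sidedness of the test, and say that the behavioral calculation concerns AHA and that task time has none.

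The cost is SAP wording and one degree of freedom per model. Design, visits and participant burden are unchanged, because the pre-test values are already collected.

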- C. Cortical Silent Periods: Twenty pulses will be delivered at the motor hotspot using a testing intensity equivalent to 120% of the MT with the target hand muscle activated.
- D. Paired-Pulse Assessment: Using two TMS coils, a conditioning stimulus will be delivered to one hemisphere at an intensity equivalent to 100% MT. Simultaneously, a test stimulus will be delivered to the opposite hemisphere at an intensity equivalent to 120% RMT. A total of 20 pairs of stimuli will be used (10 with interstimulus interval = 10 ms, ten with interstimulus interval = 0 ms), delivered in a pseudorandom order.

Pre-Test Assessment: Behavioral

We will use the Gross Motor Function Classification Scale Score (GMFCS), and the Manual Ability Classification System (MACS) as clinical characterization of each participant. Members of the research team will assess hand function using the following measures: Assisting Hand Assessment (AHA), Box and Blocks Test, Grip Strength Dynamometry, and Jebsen Taylor Test of Hand Function (JTTHF). A novel motor performance task will also be employed to assess motor performance and potential effects of tDCS on motor learning.

Intervention

The intervention will last a total of 30 minutes, including preparatory time. Before stimulation, the area of skin underneath the electrode will be inspected for abrasions/lesions and then cleaned with an alcohol swab. We will use an M1-SO electrode montage, where one tDCS electrode is placed on the motor hotspot (M1) as determined by TMS testing, and the other electrode is placed on the supraorbital prominence (SO) of the opposite side. Sanitized rubber electrodes housed in single-use, sterile 3 cm x 5 cm sponges moistened with saline will be placed on the stimulation sites and held in place by elastic bands. To ensure adequate electrical conductance, care is taken to maintain firm contact of the sponge to the scalp. The static

impedance measurement is checked and stimulation does not proceed unless levels are within limits recommended by the tDCS device manufacturer.

Children in the sham group will receive the same procedures as the active tDCS group, yet the device will be set to an integrated sham setting which extinguishes the current after a 30 second to 1 minute ramp-up phase and gradually reintroduces the ramp-down at the end of the 20 minute session.

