After the first 2 minutes of stimulation, the participant is questioned about pain at the electrode sites. If the stimulation is painful, a small amount of additional saline (2-4 mL) is added to the sponge, taking care to avoid wetting adjacent hair and thereby increasing the electrode area, and the tightness and placement of the band are checked. If pain persists, the stimulation intensity is decreased, and symptoms re-assessed. If pain still persists, stimulation is stopped and the electrode sites are checked. This procedure is repeated twice (every 5 minutes during tDCS) with saline solution (2-4 mL) added as needed.

Participants will receive a total of 20 minutes of active or sham tDCS. During stimulation, participants will practice the novel reaching task described above at a comfortable pace. No conversations between participant and researchers or caregivers will be allowed, except those that pertain to safety.

Post-intervention Assessments

Immediately following the intervention, TMS and Behavioral assessments will be performed at 0, 15, 30, and 60 minutes following the intervention (see Figure 2).

Other Procedures

Computational Modeling

Computational modeling of electric fields produced by tDCS will be performed using SimNIBS (Simulation of Non-invasive Brain Stimulation). Using T1-anatomical images, individual skull and brain anatomy will be reconstructed, and electric fields computed using a finite element method. The primary outcome is the estimated peak electric field strength for the M1-SO montage.

Safety Monitoring

We will use questionnaires (Appendix F) to document symptoms associated with non-invasive brain stimulation before and after the intervention and testing session. This tool asks participants about the presence and severity of symptoms such as tingling, itchiness, and headache. We will also measure heart rate and blood pressure before and after the procedures.

Follow-Up: A member of the research team will contact each participant and their caregivers within one week of completing the study to check for any adverse events. There is no long-term follow-up data collection planned.

- 5.3 Study Duration: Each participant will complete the study in either one day (MRI and intervention, four hours total) or on two separate days (one hour MRI, and three hours intervention). If done on two days, the MRI and intervention will be separated by no longer than a two week (14 day) period.

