17.0 Provisions to Monitor the Data to Ensure the Safety of Participants

17.1 Data Integrity Monitoring.

There will not be a designated data integrity monitor associated with this study. Instead, the PI will work with the study coordinator to ensure all data is collected, recorded, and maintained properly, and that regulatory and compliance procedures are followed accordingly.

The study case report form (CRF) is the primary data collection instrument for the study. All data requested on the CRF must be recorded. All missing data must be explained. If a space on the CRF is left blank because the procedure was not done or the question was not asked, write "N/D". If the item is not applicable to the individual case, write "N/A". All entries should be printed legibly in black ink. If any entry error has been made, to correct such an error, draw a single straight line through the incorrect entry and enter the correct data above it. All such changes must be initialed and dated. **DO NOT ERASE OR WHITE OUT ERRORS.** For clarification of illegible or uncertain entries, print the clarification above the item, then initial and date it.

A Case Report Form will be completed for each participant enrolled into the clinical study. The investigator will review, approve and sign/date each completed CRF. The investigator's signature serves as attestation that all clinical and laboratory data entered on the CRF are complete, accurate and authentic.

The CRF shall contain at a minimum the following components:

- 1) Eligibility documentation, Phone Screen Form
- 2) HIPAA Form
- 3) Demographic Medical History Form
- 4) Individual Data Collection Forms
- 5) Exit and Survey Forms

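### The repeated measures ANOVA in 15.1 has no stated time points, sphericity correction or rule for a missed round; a baseline-adjusted mixed model should replace it

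*Combined protocol and SAP*

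**What the plan says.** - **Method.** Section 15.1 states: "The primary analysis will compare changes in behavioral and neurophysiologic measures between the two intervention groups (real and sham tDCS". It then names the method: "When possible, we will use repeated measures ANOVA to account for differences between groups". It lists no time points, no effect to be tested, no significance level and no sphericity correction.
- **Schedule.** Section 5.2 states: "TMS and Behavioral assessments will be performed at 0, 15, 30, and 60 minutes following the intervention". With the pre-test, that makes five unequally spaced assessments.
- **MEP analysis.** Section 15.3 describes an intent-to-treat comparison of MEP change between each stimulation group and sham, adjusted for baseline, with robust variance and a threshold of 0.0125. On timing it says: "The primary analysis will evaluate the change between pre- and post- measurements" and "A secondary analysis will evaluate the change between pre- and 30 minutes post". The 15- and 60-minute rounds are not mentioned.
- **Incomplete data.** Section 17.1 says: "All missing data must be explained". That is an instruction for completing the case report form, not an analysis rule. Section 12.3 says that data gathered before an investigator removes a participant will still be used.

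**The concern.** Section 15.3 tests only the MEP. Time on the movement task (3.1) and the silent period, paired-pulse, Box and Blocks and grip strength outcomes (3.2) therefore depend on 15.1 for their between-group test. The fallback in 15.1 for non-normal data, the Wilcoxon signed-ranks test, is a paired test and does not compare groups. The interim safety rule in 17.2 compares sham and real performance on the reaching task against a 2 SD threshold, but it is not an efficacy test.

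The natural reading of a repeated measures method applied to this schedule is a five-time ANOVA whose group-by-time term tests differential change. That test has two weaknesses here.

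1. It assumes that all pairwise differences between times have equal variance. Measurements close together in time usually correlate more strongly than distant ones. Without a correction, the p-value is then too small.
2. In its classical form it uses only children with all five values. A child who stops after the 30-minute round loses every earlier value as well, which sits badly with 12.3. If those who stop early are the tired or uncomfortable children, the loss may also be selective.

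**Working it through.** **The plan's own figure.** Section 15.2 gives 81% power for a 0.75 mV change, SD 0.5, pre-post correlation 0.5, 8 per group and alpha 0.0125 (0.05/4).
- Adjusted SD = 0.5 × √(1 − 0.5²) = 0.433.
- Standard error = 0.433 × √(2/8) = 0.2165.
- Ratio = 0.75 / 0.2165 = 3.464.
- Two-sided normal power = Φ(3.464 − 2.498) = 0.833. A one-sided 0.0125 test with noncentral t on 13 df gives 0.811, which matches the plan.

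Either way, this is the power of a baseline-adjusted pre/post comparison. It is not a figure for a five-time ANOVA.

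**Inputs for the error-rate check.** There are two groups (15.1) and five times (5.2). The pre-test is placed 30 minutes before the first post-test because 5.2 says: "The intervention will last a total of 30 minutes, including preparatory time". The documents do not give the covariance between times, so the patterns below are assumptions.

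**Formulas.** With g = 2 groups, p = 5 times and N children:
- F = [SS(group × time) / ((g−1)(p−1))] / [SS(residual) / ((N−g)(p−1))]. For 8 v 8 the df are 4 and 56.
- Epsilon = tr(M)² / ((p−1) tr(M²)), where M is the double-centred covariance matrix. Greenhouse-Geisser multiplies both df by the estimated epsilon.

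**Results.** Null simulation, normal data, 8 v 8, 40,000 trials per pattern (simulation standard error about 0.001 or less):

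| Assumed correlation | Epsilon | Uncorrected, nominal 0.05 | Uncorrected, nominal 0.0125 | Greenhouse-Geisser, nominal 0.0125 |
|---|---|---|---|---|
| Compound symmetry, 0.5 | 1.00 | 0.049 | 0.012 | 0.006 |
| 0.5 per 30 min | 0.78 | 0.066 | 0.021 | 0.009 |
| 0.7 per 30 min | 0.69 | 0.073 | 0.027 | 0.011 |
| 0.9 per step | 0.58 | 0.081 | 0.034 | 0.013 |

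With 20 v 20, the three serial patterns give 0.062 to 0.079 at nominal 0.05 and 0.021 to 0.034 at nominal 0.0125, so a larger sample does not cure the problem. A steeper pattern (pre-post 0.5, post-post 0.9; epsilon 0.47) gives 0.093 and 0.046. The range above is therefore not an upper bound.

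**What stays correct.** Under the patterns in the table, the ANOVA group main effect runs at 0.012 to 0.013 for nominal 0.0125, and so does a two-time change comparison. With two times there is only one difference, so sphericity cannot fail.

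**Children dropped.** Assume that the pre-test is always obtained and that each of the four post rounds is missed independently with probability q. The share dropped is 1 − (1−q)⁴.

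| q | Share dropped | Left of 8 |
|---|---|---|
| 0.2% | 0.8% | 7.9 |
| 2% | 8% | 7.4 |
| 5% | 19% | 6.5 |
| 10% | 34% | 5.2 |

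The 0.2% row borrows the 99.8% adherence in 11.1. That figure concerns visits, not rounds within one session.

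**The case against.** The strongest case is that 15.1 is only a sketch. It hedges with a condition, does not say that five times enter, does not name group-by-time as the test, and does not say that incomplete children are dropped. Unequal spacing is not in itself a sphericity violation. The correlations and missingness rates are assumed, and the laboratory reports 100% retention of 50 children in three earlier studies. All of this is right, and it is why the size is conditional and given as a range. It does not remove the gap, because no other section supplies a test for these outcomes and times.

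Three stronger readings are tempting, and the documents do not support them.

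- **That the 0.0125 test in 15.3 has its error rate doubled.** The 0.0125 is 0.05 divided by four arm comparisons, and 15.3 applies it to baseline-adjusted MEP change at one post time. Sphericity does not arise there. Section 15.1 states no alpha. If its outcomes are tested at 0.05, the inflation in the table is 1.3 to 1.6 times (0.066/0.05 to 0.081/0.05), not double.
- **That the plan contradicts its intent-to-treat statement.** The sentence "This analysis will be conducted based on the intent-to-treat principle" belongs to the MEP analysis in 15.3. A child who misses only a later round stays in that analysis. The real tension is between complete-case ANOVA and 12.3.
- **That the 81% power is overstated because of missed rounds.** That figure needs only the pre value and one post value. Five-time complete-case losses do not apply to it.

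**Conclusion.** The point holds in a limited form. For task time, the secondary neurophysiological and behavioral outcomes, and the 15- and 60-minute MEP rounds, the only between-group method stated is one that is too liberal under plausible serial correlation and that discards incomplete children.

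The size rests on three assumptions: that all five times enter, that the group-by-time term is the test, and that correlation falls with distance in time as in the patterns shown. On those terms, nominal 0.05 runs at about 0.06 to 0.08 and nominal 0.0125 at about 0.02 to 0.035. If compound symmetry held, there would be no inflation. The loss of children could be trivial (under 1%) or substantial (about a third), depending on a within-session rate that the documents do not give.

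The change should be made because the better method costs little. The MEP contrasts in 15.3 and their stated power stand apart from this point.

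**What to change.** In 15.1, replace repeated measures ANOVA with a linear mixed model:

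- **Response:** all observed values at 0, 15, 30 and 60 minutes.
- **Fixed effects:** arm, time, arm-by-time, the baseline value and baseline-by-time.
- **Estimation:** REML with Kenward-Roger degrees of freedom and an unstructured within-child covariance. Name a simpler fallback in advance, such as heterogeneous autoregressive, for use if the unstructured form cannot be estimated.
- **Contrast:** the arm difference at the post time named in 15.3, with the other times secondary. State which round 15.3 means by post; the 0-minute round is the natural reading, since 30 minutes is named separately as secondary.

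The baseline terms matter. Without baseline adjustment, at SD 0.5 and 8 per group, the ratio is 0.75 / (0.5 × √(2/8)) = 3.0 and two-sided normal power is Φ(3.0 − 2.498) = 0.69, against 0.83 with adjustment at correlation 0.5.

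If ANOVA is kept for any outcome with more than two times, state the times, the effect tested, the Greenhouse-Geisser correction and the handling of missed rounds.

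**Cost:** plan wording and standard software, with no new data. Intervals will be slightly wider than from an uncorrected ANOVA. The fallback covariance must be fixed beforehand, because a poorly chosen simple structure can bring the same error back. The model uses partial data validly only if missed rounds depend on observed values. At 8 v 8, Greenhouse-Geisser is conservative when sphericity does hold (0.006 at nominal 0.0125).
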